3. DESCRIPTION OF DESIGN AND TRIAL POPULATION

3.1 OVERALL TRIAL DESIGN AND PLAN

This trial is a prospective, randomised, double-blind, parallel group, multi-centre trial to show superiority in terms of reduction of Pain on Movement (POM) of a topical combination containing diclofenac 2% and capsaicin 0.075% compared to placebo, as well as to diclofenac 2% and capsaicin 0.075% when applied twice daily over 4 to 7 days to patients with acute back pain or neck pain. A total of approximately 800 patients will be randomised to the treatment groups diclofenac + capsaicin, diclofenac, capsaicin and placebo in a 3:3:3:1 ratio in order to achieve 700 patients eligible for the assessment of the primary endpoint.

After a screening evaluation (Visit 1), eligible patients will be randomised into the double-blind treatment phase of the trial. After administration of the first treatment, the patients will administer the second application of the trial medication in the evening at home. They will return to the trial site for four more visits (Visits 2 to 5) in the morning and in the evening of the following day (Day 2) and in the morning of Days 3 and 4 and thereby be dosed while at the site. Evening applications on Day 3 and Day 4 will be administered by the patients at home. Thereafter, the treatment will be administered at home for one more day (Day 5). The patients will then return to the trial site for final assessments (Visit 6) in the morning of Day 6. The trial participation will be concluded by a telephone call (Visit 7T) for follow-up on adverse events (AEs) on Day 8.

Depending on the severity of a patient's condition and on a patient's availability, the treatment-period at home (Day 5) could be skipped or extended by one or two days. Visit 6 should then be performed on the day immediately following to that shortened or extended period.

The interval between two applications of the trial medication should be 12 hours. This interval could be shortened or extended by 4 hours as long as no more and no less than two applications are administered on each treatment day.

Patients who discontinue the application of the trial medication prematurely, should be encouraged to contact the site immediately so that Visits 6 and 7T could be performed on the day immediately after discontinuation.

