6. INVESTIGATIONAL PLAN

6.1 VISIT SCHEDULE

This trial consists of 6 clinical visits. For the follow-up contact (Visit 7T) the investigator will contact the patient by phone.

If a Visit 2-5 is missed, it should not be re-scheduled. However subsequent visits should follow the original visit schedule. If Visit 6 or Visit 7T is missed, this visit should be rescheduled to the closest opportunity.

All trial visits except for Visit 3 should take place in the morning, i.e. ideally be started and completed between 7:00 a.m. and 11:00 a.m. Patients must adhere to the visit schedule as specified in the Flow Chart. Visits 2 (Day 2 morning) and 3 (Day 2 evening) need to be scheduled such that the trial medication could be applied according to the required dosing interval of 12 hours (± 4 hours).

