7.3.2 Secondary endpoint analyses

The key secondary and other secondary endpoints will be analysed with the treated set as defined for efficacy analysis in Section 7.3.

The key secondary endpoints of $POM_{WP}AUC_{72}$ and $POM_{WP}AUC_{120}$ will be analysed using an analysis of covariance (ANCOVA) including treatment, country and application site (back/neck) as fixed effects and the baseline POM_{WP} as a continuous covariate. Treatment differences will be estimated by reference to the adjusted least square means and the corresponding 95% confidence intervals. The statistical testing will be performed using a two-sided, alpha = 0.05 level of significance.

The number of patients with a decrease in POM_{WP} of at least 30% from baseline until Day 2 evening, 1 hour after drug application, will be analysed by a logistic regression model, adjusting for the categorical covariates country and application site (back/neck). The likelihood-ratio test will be used to test for differences between treatments. Adjusted odds ratios together with 95% confidence intervals will be used to quantify the effect of treatment, comparing all treatments to the treatment of diclofenac/capsaicin as the reference treatment.

The number of patients with a decrease in POM_{WP} of at least 50% from baseline until Day 2 evening, 1h after drug application, will be analysed correspondingly.

The change in POM_{WP} between baseline and the morning of Day 6 will be analysed analogously to the primary endpoint. The statistical model will be applied to the analysis of change from baseline (T0 = Visit 1 morning, before application) in POM_{WP} at times T1, T3, T4, T5 and - additionally at times T7 (=Visit 4 = Day 3 morning, 1 hour after application), T9 (= Visit 5 = Day 4 morning, 1 hour after application) and T12 (= Visit 6 = morning of Day 6).

The change in PA between baseline and Day 2 evening, before drug application (Visit 3) will be analysed analogously to the primary endpoint using all available longitudinal PA observations at the assessment times T2 = Visit 2 (Day 2 morning, before application) and T4 = Visit 3 (Day 2, evening, before application). The statistical model will be applied to the analysis of change from baseline (T0 = Visit 1 morning, before application) in PA at times T2 and T4.

The change in PA between baseline and the morning of Day 6 will be analysed analogously to the primary endpoint. The statistical model will be applied to the analysis of change from

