7.5 HANDLING OF MISSING DATA

Every effort should be made to collect the complete data at the planned time points for this trial.

For the analyses utilising a likelihood-based repeated measures model as described in Section 7.3, no imputation of missing values will be performed.

Missing entries for the assessment of efficacy will be assigned the least favourable category if missing was the result of discontinuation due to lack of efficacy. Missing entries for the assessment of tolerability will be assigned the least favourable category if missing was the result of discontinuation due to drug-related adverse events.

Missing patient assessments of efficacy or tolerability resulting from early discontinuation that was clearly unconnected to treatment will be not imputed.

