6.6.2 Missing efficacy data

Every effort should be made to collect complete data for each time point at each test day, independent whether it is related to POM_{WP} endpoint data or any other endpoint data.

For missing baseline data, no imputation will be implemented.

For the analyses utilising a likelihood-based repeated measures model, no imputation of missing values will be performed.

For details on the handling of missing data for the AUC calculation see section 5.2.1.

Missing patient assessments of resulting from early discontinuation that was clearly unconnected to treatment will not be imputed.

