7. PLANNED ANALYSIS

For End-of-Text (EoT) tables, for continuous variables, the set of summary statistics is: Number of patients with non-missing values / Mean / standard deviation (SD) / Minimum / Q1 (lower quartile) / Median / Q3 (upper quartile) / Maximum.

Tabulations of frequencies for categorical and ordinal data will include all possible categories and will display the number of observations in a category as well as the percentage (%) relative to the respective treatment group (unless otherwise specified, all patients in the respective patient set whether they have non-missing values or not). Percentages will be rounded to one decimal place. The category missing will be displayed only if there are actually missing values.

Patient sets for the planned analyses are displayed in Table 6.3: 1. Patient data listings (PDLs) will be based on the randomised set. If any AEs/SAEs are reported for screening failures, these will be summarised in the AE listing "Adverse event overall summary" and described in the Clinical Trial Report (CTR) if considered related to the screening procedures.

For all efficacy analyses pertinent to application site and applicable only to the FAS and any patient who is incorrectly randomised into the stratum not containing the POM_{WP} will be included in the stratum with the POM_{WP} .

As detailed in Section 4 all analyses pertaining to POM will be performed on the normalised POM scores derived as:

Normalised POM score (cm) = $\frac{POM \text{ score}}{VAS \text{ scale length}}$ x 10

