7.5.2.1 Endpoints from POM_{WP}

The number of patients with a decrease in POM_{WP} of at least 30% from baseline until day 2 evening, 1h after drug application, will be analysed using a logistic regression model as described in the CTP. Treatment differences will be analysed using adjusted odds ratios which will be presented together with 95% confidence intervals, the combination treatment (diclofenac and capsaicin) will be used as the reference treatment. Odds ratios will be

[figure not shown]
calculated as combination treatment/individual treatments or placebo, meaning an odds ratio >1 would indicate better responses for the combination treatment.

The number of patients with a decrease in POM_{WP} of at least 50% from baseline until day 2 evening, 1h after drug application, will be analysed similarly.

Change in POM_{WP} between baseline and the morning of day 6 will be analysed analogously to the primary endpoint, using all available data points as described in CTP section 7.3.2.

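### Do the supportive 30%/50% responder analyses need a different reference arm or a written rule for missing Visit 3 values?

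*Protocol*

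**What the plan says.** Protocol 7.3.2 analyses the proportion of patients whose POM_WP has fallen by at least 30% (and, likewise, 50%) at Visit 3, one hour after the evening application. The model is a logistic regression adjusted for country and application site. Results are adjusted odds ratios, "comparing all treatments to the treatment of diclofenac/capsaicin as the reference treatment". SAP 7.5.2.1 repeats that "the combination treatment (diclofenac and capsaicin) will be used as the reference treatment" and then states that the ratios are "calculated as combination treatment/individual treatments or placebo, meaning an odds ratio >1 would indicate better responses for the combination treatment".

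Both documents use the treated set, which requires one dose but no post-baseline pain score. The text on missing data is spread over several places:

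- SAP 6.6.2: "For the analyses utilising a likelihood-based repeated measures model, no imputation of missing values will be performed". It refers to SAP 5.2.1 for the AUCs and leaves values unimputed after discontinuation clearly unrelated to treatment.
- Protocol 7.5: missing efficacy entries are "assigned the least favourable category if missing was the result of discontinuation due to lack of efficacy". There is a parallel rule for tolerability entries after drug-related adverse events, and no imputation after stops clearly unrelated to treatment.
- SAP 6.3: the number of patients with data may differ by endpoint, with a pointer to section 6.6.
- SAP 7: unless otherwise specified, percentages are relative to "all patients in the respective patient set whether they have non-missing values or not", and a missing category is shown when values are missing.

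Protocol 7.2 treats these endpoints as supportive only.

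**The concern.** Two things look wrong. First, a reference level is normally the denominator of an odds ratio. A programmer who declares the combination as the reference level gets comparator/combination. If that output is then read with the SAP's rule that values above 1 favour the combination, a benefit appears as harm.

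Second, some treated patients will have no Visit 3 value. Those who stop early are asked to contact the site "so that Visits 6 and 7T could be performed on the day immediately after discontinuation", and for the others "If a Visit 2-5 is missed, it should not be re-scheduled". An ordinary logistic fit drops both groups without comment, while a frequency table on the SAP's default denominator keeps them. If drug-related stops before Visit 3 were more common with the capsaicin-containing gels, the observed-case odds ratio would flatter the combination. The effect would be largest against placebo, smaller against diclofenac and close to nil against capsaicin gel.

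**Working it through.** **Inputs.** The plan gives no power, response rate or early-dropout rate for the responder endpoints, so there is no stated figure to reproduce. From Protocol 7.7: 210, 210, 210 and 70 evaluable patients, and about 800 randomised for 700 evaluable. The primary-endpoint power with these arm sizes does reproduce: 98.3% and 82.3% by the noncentral t, against the stated 98% and 82%. All response and loss rates below are assumptions.

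**1. Direction of the ratio.** Take 126/210 responders on the combination and 105/210 on a comparator.

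- Combination/comparator: (126/84)/(105/105) = 1.50.
- Standard error of the log odds ratio: √(1/126 + 1/84 + 1/105 + 1/105) = 0.197.
- z = ln(1.50)/0.197 = 2.06, p = 0.040, 95% CI 1.02 to 2.21.
- Comparator/combination: 1/1.50 = 0.67, 95% CI 0.45 to 0.98, p = 0.040.

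The two codings are exact reciprocals with the same test. Protocol 7.3.2 names the common comparison arm but no numerator. SAP 7.5.2.1 names the numerator, the denominator and the favourable direction. Following the SAP sentence gives 1.50.

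**2. Missing Visit 3 values.** Let p be the response rate among observed patients and l the fraction lost for drug-related reasons, with subscripts c for the combination and k for the comparator. Counting those losses as non-response gives

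OR = odds[p_c(1 − l_c)] / odds[p_k(1 − l_k)], where odds[x] = x/(1 − x).

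Example with 60% v 50% and losses of 3% v 1%: odds(0.582)/odds(0.495) = 1.392/0.980 = 1.420. The observed-case value of 1.50 is 1.50/1.420 = 1.056 times this, an overstatement of 5.6%.

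| Loss, combination v comparator | OR at 60% v 50% (observed 1.50) | Overstatement | OR at 40% v 30% (observed 1.556) | Overstatement |
|---|---|---|---|---|
| 1% v 0% | 1.463 | 2.5% | 1.530 | 1.7% |
| 3% v 1% | 1.420 | 5.6% | 1.501 | 3.7% |
| 5% v 0% | 1.326 | 13% | 1.430 | 8.8% |
| 3% v 3% | 1.478 | 1.5% | 1.545 | 0.7% |
| 5% v 5% | 1.465 | 2.4% | 1.538 | 1.2% |

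The equal-loss rows stand for the comparison with capsaicin gel. For scale, the largest shift is ln(1.50/1.326) = 0.12 on the log scale. Against placebo (210 v 70) the standard error is √(1/126 + 1/84 + 1/35 + 1/35) = 0.28, so the shift is well under half a standard error. Against a single component (210 v 210) it is 0.12/0.197, about 0.6 of one.

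**3. A stress case.** Assume 60% v 45% response, 240 treated per arm, and every missing patient counted as a non-responder. The observed-case OR is 1.83 (1.24 to 2.70, at 210 per arm).

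- 30 missing in each arm: 1.70 (1.18 to 2.44).
- 40 on the combination, 20 on the comparator: (120/120)/(99/141) = 1.42 (0.99 to 2.04).
- 20 and 40: (132/108)/(90/150) = 2.04 (1.41 to 2.93).

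Unequal loss on that scale would matter, in either direction.

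**4. Is that scale foreseen?** The allowance is 1 − 700/800 = 12.5%, or 30 patients per active arm. It is not a forecast of missing Visit 3 values. It is measured from randomisation, whereas the treated set leaves out untreated patients. Also, the full analysis set admits anyone with a single post-baseline score up to Visit 3, so a patient can be evaluable for the primary analysis and still lack the Visit 3 value. If all 12.5% were missing at Visit 3, 126 responders would be 126/210 = 60.0% in the model and 126/240 = 52.5% in a table, with the difference shown in the missing category.

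**The case for a change.** The best case for a change is that the wording does conflict with ordinary usage and that direction slips do occur: SAP section 4 records that change from baseline was programmed with the opposite sign to the protocol and left that way. The missing-data rule can also move the estimate, and in the stress case it moves the lower confidence limit from above 1 to just below it. No visible sentence covers a Visit 3 missed while on treatment, or an efficacy value lost after an adverse-event stop. A few lines written before unblinding would remove the choice from the analyst.

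The narrow gap stands; the rest is weaker. On direction, the sign reversal was noticed and documented, and the SAP states the favourable direction for both the primary contrast and the odds ratios. Responder counts by arm would expose an inverted ratio at once.

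On missing values, Protocol 7.5 can be read as covering stops for lack of efficacy and stops unrelated to treatment, although it may have been written for a categorical rating. The matching sentence in SAP 6.6.2 is visibly incomplete, and SAP section 9, which holds the analysis code for the primary endpoint, is not in the public text. An absent rule therefore cannot be firmly inferred.

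Counting drug-related adverse-event stops as efficacy failures would not be a neutral repair. Protocol 7.5 ties those stops to the worst tolerability category and lack of efficacy to the worst efficacy category. Merging the two is a different estimand, and a debatable one.

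**Conclusion.** No change is called for. The reference-arm label is a clerical looseness: the SAP's explicit ratio governs, the p-value is identical, and following the SAP gives the intended result. The missing-value point is a small gap that analysts fill sensibly, with available data as the natural default given SAP 6.3 and the number of patients contributing shown beside the odds ratio. The table and the model may rest on different counts, but the SAP's default display of a missing category makes that visible.

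Under assumed drug-related losses of up to 5%, the convention moves the odds ratio by 0.7% to 13%, and by no more than 2.4% against capsaicin gel. Larger unequal losses could move it further, but nothing in the documents points to them. These sizes rest wholly on assumed response and dropout rates. The endpoints are supportive, so the primary comparison, the key secondary tests, the type I error rate and the sample size are unaffected.

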7.3.4 Safety analyses

Adverse events will be coded using the Medical Dictionary for Regulatory Activities (MedDRA) coding dictionary. Standard BI summary tables and listings will be produced. All adverse events with an onset between start of treatment and end of the REP, a period of 48 hours after the last application of trial medication, will be assigned to the treatment period for evaluation.

All treated patients will be included in the safety analysis. In general, safety analyses will be descriptive in nature and will be based on BI standards. No hypothesis testing is planned. Safety analyses will be done by the actual treatment as defined for safety analysis in Section 7.3.

Statistical analysis and reporting of adverse events will concentrate on treatment-emergent adverse events. To this end, all adverse events occurring between start of treatment and end of the residual effect period will be considered 'treatment-emergent'. The residual effect period is defined as a period of 2 days (48 hours) after the last application of trial medication. Adverse events that start before first drug intake and deteriorate under treatment will also be considered as 'treatment-emergent'.

Frequency, severity, and causal relationship of adverse events will be tabulated by system organ class and preferred term after coding according to the current version of the Medical Dictionary for Drug Regulatory Activities (MedDRA).

Laboratory data will be analysed both quantitatively as well as qualitatively. The latter will be done via comparison of laboratory data to their reference ranges. Values outside the reference range as well as values defined as clinically relevant will be highlighted in the listings. Treatment groups will be compared descriptively with regard to distribution parameters as well as with regard to frequency and percentage of patients with abnormal values or clinically relevant abnormal values.

Vital signs, physical examinations, or other safety-relevant data observed at screening, baseline, during the course of the trial and at the end-of-trial evaluation will be assessed with regard to possible changes compared to findings before start of treatment.

The final overall patient / investigator assessment of tolerability will be analysed analogously to

The assessment of skin reactions will be analysed descriptively.

7.4 **INTERIM ANALYSES**

No interim analysis is planned.

c03317678-02 Trial Protocol Page 53 of 69

7.5 HANDLING OF MISSING DATA

Every effort should be made to collect the complete data at the planned time points for this trial.

For the analyses utilising a likelihood-based repeated measures model as described in Section 7.3, no imputation of missing values will be performed.

Missing entries for the assessment of efficacy will be assigned the least favourable category if missing was the result of discontinuation due to lack of efficacy. Missing entries for the assessment of tolerability will be assigned the least favourable category if missing was the result of discontinuation due to drug-related adverse events.

Missing patient assessments of efficacy or tolerability resulting from early discontinuation that was clearly unconnected to treatment will be not imputed.

7.6 RANDOMISATION

Patients will be randomized in blocks to double-blind treatment arms diclofenac + capsaicin, diclofenac, capsaicin and placebo in a ratio 3:3:3:1. The randomization allocation will be stratified by country (Russia, Germany) and application site (back/neck). At least 40% of the randomised total population are aimed to be patients with neck/back pain, respectively. For further details on the stratified randomisation see Section 4.1.2.

BI will arrange for the randomization and the packaging and labelling of trial medication. The randomization list will be generated using a validated system, which involves a pseudorandom number generator so that the resulting treatment will be both reproducible and non-predictable. The block size will be documented in the Clinical Trial Report (CTR). Access to the codes will be controlled and documented.

7.7 DETERMINATION OF SAMPLE SIZE

The sample size calculation is based on the assumption of superiority of the combination diclofenac + capsaicin versus diclofenac, capsaicin and placebo with regard to the primary efficacy variable 'Change in POM_{WP} between baseline (before application at Visit 1) and Visit 3 (Day 2 evening, 1 hour after application)', which reflects a pain relief on a 0-100 mm VAS about 36 h after baseline.

In a previous study investigating diclofenac in comparison to placebo in patients with acute neck pain, the true treatment difference in POM 48 h after baseline was assumed to be 12 mm [R14-1467] In another study comparing the effects of a combination of comfrey root extract with methyl nicotinate in patients with acute back pain, the standardized difference between the combination and a single ingredient was assumed to be 0.4 [R12-4427].

The sample size for this study is based on an anticipated treatment difference of 12 mm on a 0-100 mm VAS and a common standard deviation of 30 mm, yielding a standardized treatment difference of 0.4 concerning the primary endpoint. The allocation ratio to the

c03317678-02

Page 54 of 69

Proprietary confidential information © 2016 Boehringer Ingelheim International GmbH or one or more of its affiliated companies

treatment groups diclofenac + capsaicin, diclofenac, capsaicin and placebo is planned to be 3:3:3:1.

A total sample size of 700 patients (210 patients with diclofenac + capsaicin, diclofenac and capsaicin, respectively and 70 patients with placebo will have 98% power to detect a difference of 12 mm on a 0-100 mm VAS for the primary endpoint between treatment effects of diclofenac + capsaicin versus diclofenac and capsaicin, respectively (3:3 allocation ratio) and 82% power to detect the same difference between diclofenac + capsaicin and placebo (3:1 allocation ratio), assuming a common standard deviation of 30 mm and using a 0.05 two-sided significance level.

The total sample size of 700 patients will reach statistical significance with 95% confidence in the 3:3 comparisons (diclofenac + capsaicin versus diclofenac and capsaicin, respectively), when the observed treatment difference is at least 5.7 mm, and in the 3:1 comparison (diclofenac + capsaicin versus placebo), when the observed treatment difference is at least 8.1 mm.

About 800 patients will be randomised to ensure that 700 patients are evaluable for the primary endpoint; as soon as 700 patients in total are evaluable for the primary analysis, the randomisation will be stopped. To ensure that each application site stratum "back pain" or "neck pain" is represented by at least 40% of the randomised patients, randomisation into a respective stratum will be capped as soon as 60% of the total trial population have been allocated to the respective stratum.

Calculations were performed using nQuery Advisor® 6.1 statistical package by Statistical Solutions Ltd.

Proprietary confidential information © 2016 Boehringer Ingelheim International GmbH or one or more of its affiliated companies

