3.3 SELECTION OF TRIAL POPULATION

A sufficient number of patients with acute back or neck pain will be screened. It is assumed that approximately 800 patients will need to be randomized at around 20 trial sites to achieve 700 patients who are evaluable with regard to the primary endpoint.

It is expected that around 40 patients will be randomised at each trial site. If enrolment is delayed, additional sites may be recruited. Permission to randomise more than 80 patients per site must be obtained from the Trial Clinical Monitor (TCM) at BI. This will only be allowed after a careful review of the enrolment status and of the site.

Screening of patients for this trial is competitive across all countries and sites within the trial, i.e. screening for the trial will stop at all sites when it is anticipated that a sufficient number of patients have been screened to yield the desired number of patients randomised to trial treatment. Investigators will be notified when sufficient patients have been screened and when screening is complete, and will not be allowed to recruit additional patients for the study.

Trial Protocol

c03317678-02 Page 20 of 69

Proprietary confidential information © 2016 Boehringer Ingelheim International GmbH or one or more of its affiliated companies

A log of all patients enrolled into the trial (i.e. who have signed informed consent) will be maintained in the ISF at the investigational site irrespective of whether they have been treated with investigational drug or not.

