7.3 PLANNED ANALYSES

Three analysis datasets will be defined for the purpose of summarizing and analysing the trial data.

Treated set (TS): All randomised patients who used at least one dose of study medication will be included in the treated set. Patients having received the wrong treatment will be analysed within the planned (randomised) treatment group in the efficacy analysis and within the actual treatment group in the safety analysis.

Full analysis set (FAS): All patients included in the treated set, which provide a baseline value before application for POM_{WP} at Visit 1 and at least one POM_{WP} value during the assessment times Visit 1 (Day 1 morning, 1 hour after application), Visit 2 (Day 2, morning, 1 hour after application), Visit 3 (Day 2 evening, before application), Visit 3 (Day 2 evening, 1 hour after application), will constitute the full analysis set.

Proprietary confidential information © 2016 Boehringer Ingelheim International GmbH or one or more of its affiliated companies

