7.3.1 Primary endpoint analyses

The primary endpoint 'Change in POM_{WP} between baseline (before application at Visit 1) and Visit 3 (Day 2 evening, 1 hour after application)' will be analysed utilising a restricted maximum likelihood (REML) based repeated measures approach, using all available longitudinal POM_{WP} observations at the assessment times T1 = Visit 1 (Day 1 morning, 1 hour after application), T3 = Visit 2 (Day 2, morning, 1 hour after application, T4 = Visit 3 (Day 2 evening, before application) and T5 = Visit 3 (Day 2 evening, 1 hour after application). The statistical model will be applied to the analysis of change from baseline (T0 = Visit 1 morning, before application) in POM_{WP} at times T1, T3, T4 and T5. The statistical model will include the fixed, categorical effects of treatment, country, application site (back/neck), time and treatment-by-time interaction, as well as the continuous, fixed covariates of baseline POM_{WP} and baseline-by-time interaction. The definition of baseline POM_{WP} is given in Section 7.1.

An unstructured covariance structure will be used to model the within-patient errors. In case this analysis fails to converge, other covariance structures to be employed will include Compound Symmetry, Autoregressive Model, AR (1) and Spatial Covariance, with the covariance structure converging to the best fit, as determined by Akaike's information criterion, to be used for purposes of comparing treatment effects. The Kenward-Roger approximation will be used to estimate the denominator degrees of freedom [R11-1488].

Differences between the treatment group effects (diclofenac/capsaicin - diclofenac, diclofenac/capsaicin - capsaicin, diclofenac/capsaicin - placebo) with regard to the change in POM_{WP} between T0 and T5, calculated as ' POM_{WP} at time T0 - POM_{WP} at time T5' (see Section 5.1) will be estimated by reference to the adjusted least square means and the corresponding 95% confidence intervals (CI). All statistical testing will be performed using a two-sided, alpha = 0.05 level of significance.

The primary analysis will be based on the full analysis set (FAS) as defined in Section 7.3.

In addition to the primary analysis, a separate analysis will be performed to test the heterogeneity of the strata 'application site' and 'country', respectively. In these models the two interaction terms treatment-by-stratum-by- time and stratum-by-time will be added to the primary model, respectively.

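### Could randomisation stop with fewer than 700 Visit 3 scores because Protocol 7.7 switches from the primary endpoint to the primary analysis?

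*Protocol*

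**What the plan says.** Protocol 7.7 states the target and the stop in one sentence. The first half reads "About 800 patients will be randomised to ensure that 700 patients are evaluable for the primary endpoint"; the second half says "as soon as 700 patients in total are evaluable for the primary analysis, the randomisation will be stopped".

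Section 3.1 randomises about 800 "in order to achieve 700 patients eligible for the assessment of the primary endpoint", and Section 3.3 speaks of "700 patients who are evaluable with regard to the primary endpoint". The power statement in 7.7 is for the change from baseline to Visit 3, 1 hour after application, with arms of 210, 210, 210 and 70. It gives 98% against each single component and "82% power to detect the same difference between diclofenac + capsaicin and placebo (3:1 allocation ratio").

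Section 7.3.1 runs the primary analysis on the FAS. Section 7.3 admits a treated patient to the FAS with a baseline POM_WP and at least one of four later scores, the first taken 1 hour after the first application. SAP 6.3 and 7.4.1 keep this and add nothing about when enrolment ends.

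Sections 4.1.2 and 7.7 cap each application-site stratum at 60% of the total trial population. Section 7.6 describes 40% per stratum as an aim.

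**The concern.** The two halves of the sentence use different nouns, *endpoint* and *analysis*. The only population attached to the primary analysis is the FAS, and a patient can enter it without a Visit 3 score. If the stop were run on FAS membership, such patients would count towards 700 and not be replaced.

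The protocol can produce them. A missed Visit 2 to 5 is not rescheduled (6.1), the Flow Chart gives Visit 3 no window, and early discontinuers go to Visit 6, which is not a time point in the primary model.

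At stake is power. All three comparisons must succeed (7.2), and the placebo comparison, with 70 patients, has the least to spare. Section 3.3 also seems to offer another trigger, since screening ends when enough patients have been screened "to yield the desired number of patients randomised to trial treatment". The stratum cap raises a similar doubt: it is a percentage of a total that may end anywhere from 700 to about 800.

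**Working it through.** **Inputs.** From Protocol 7.7: difference 12 mm, SD 30 mm, two-sided 0.05, arms 210/210/210/70. The share *m* of FAS patients without the Visit 3 score is assumed, because the documents give no rate.

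**1. The plan's own figures.** Two-sample t test with non-centrality 12 / [30 × √(1/n₁ + 1/n₂)].
- 210 v 210: 12 / 2.928 = 4.10, power 98.3% (stated 98%).
- 210 v 70: 12 / 4.140 = 2.90, power 82.3% (stated 82%).
- Smallest significant differences: 1.96 × 2.928 = 5.7 mm and 1.96 × 4.140 = 8.1 mm, as stated.

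The sample-size arithmetic is correct.

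**2. If the stop counted FAS members.** Visit 3 scores number 700 × (1 − *m*), with the arms scaled alike and nobody else contributing. The last column is from simulation.

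| *m* (assumed) | Visit 3 scores | v each component | v placebo | all three |
|---|---|---|---|---|
| 0 | 700 | 98.3% | 82.3% | 81% |
| 2% | 686 | 98.2% | 81.6% | 80% |
| 5% | 665 | 97.9% | 80.4% | 79% |
| 12.5% | 612 | 96.9% | 77.0% | 74–75% |

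Power against placebo reaches 80% at *m* of about 5.9%.

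**3. What the planned model recovers.** FAS patients without the Visit 3 score still supply earlier scores to the repeated-measures model. With assumed within-patient correlations of 0.3 to 0.7 and data missing completely at random, power against placebo is 80.4–81.6% at *m* = 5% and 77.1–80.3% at 12.5%.

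**4. Which reading the figures support.** The allowance is 1 − 700/800 = 12.5%. On the endpoint reading it covers patients lost before Day 2 evening. On the FAS reading it would have to cover patients with no POM_WP score at any of four time points, the first an hour after the first application and at the same visit. Losing 100 of 800 that way is implausible. Reaching 700 Visit 3 scores takes 700/0.98 ≈ 715 FAS patients at 2% missing and 700/0.95 ≈ 737 at 5%, both inside the planned 800.

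**5. The cap.** Suppose 60% is set on 800 (480 places) and one stratum fills. The smaller stratum is then (N − 480)/N: 31.4% at N = 700, 33.3% at 720, 36.0% at 750 and 40.0% at 800. Set on 700 (420 places), it is 40.0%, 41.7%, 44.0% and 47.5%.

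**6. Section 3.3.** Its screening rule forecasts when enough patients have been screened to give the number to be randomised. The same section puts that number at about 800 for 700 evaluable, so it agrees with 7.7.

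**The case for a change.** The best case for a change is that a rule ending enrolment should have one meaning and that defining evaluable would cost a line of text. The 82% has little slack, joint power is already about 81%, and the literal chain from 7.7 through 7.3.1 to 7.3 does lead to the FAS. A cap meant to secure 40% per stratum can miss it if it is fixed on 800 and enrolment ends earlier.

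What stands is that the two nouns differ and evaluable is undefined in the available text. The rest is weaker:

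- The larger power loss needs one FAS patient in eight to lack a score due about 37 hours after the first application. Nothing in the documents supports that rate. It also places the whole allowance inside the FAS.
- The 82% assumes that the combination beats placebo by the same 12 mm as it beats each component, so that the components add nothing over placebo. If the margin over placebo were 13 mm or 14 mm (illustrative values), power at 12.5% missing would be 83.3% or 88.3%.
- On the cap, a base is named, the total trial population, and Sections 7.6 and 7.7 link it to randomised patients. The number entered is a setting for the randomisation system, whose manual lies outside these documents. The 31% needs one stratum to fill 480 places and every randomised patient to be evaluable, so that randomisation stops at exactly 700. No visible power claim rests on stratum size; application site is a stratification factor and model term. Fixing the cap at 420 would force 47.5% into the smaller stratum at 800, stricter than the protocol's 60/40, and could slow recruitment.

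**Conclusion.** No change to the plan follows. The mismatch is loose wording inside one sentence, and the context settles it: the first half of that sentence, Sections 3.1 and 3.3 and the power calculation all set the 700 on the primary endpoint. A trial team would count Visit 3 scores.

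If it counted FAS members instead, the cost would be about 1 to 2 percentage points of power against placebo at an assumed 2% to 5% missing, before the model recovers part of it. Power against each component would stay at 96.9% or more even at 12.5%. The count that ends enrolment does not depend on treatment or outcome comparisons, so the type I error and the treatment estimates are unaffected on either reading.

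The cap is a trade-off between balance and recruitment with no effect on the primary conclusion. This judgement rests on the missing rate being in the low single figures, which the documents neither state nor contradict. At 12.5% the FAS reading would take power against placebo to about 77–80%.
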